2.7. Study Hypothesis and Anticipated Results

Prophylactic ceftriaxone administered within six hours of ICU admission will reduce the incidence of EOP and T cell-mediated inflammation in comatose OHCA survivors. Additionally, prophylactic ceftriaxone will not negatively affect bacterial resistomes as assessed by resistance genotypes in stool or sputum.

3. Trial Design

The PROTECT trial was a single-center, randomized-controlled, quadruple-blind, non-commercial superiority trial conducted at xxxx. The inflammation analysis will be completed at xxxx. The resistome analysis will be done at xxxx and xxxx.

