9.2. Primary Efficacy Outcome

Success of randomization will be assessed by comparing baseline characteristics of patients in the drug and placebo groups, using standard descriptive statistics, means and standard deviations or medians and interquartile ranges, as appropriate for continuous variables and proportions for categorical variables. No p values will be presented as is typical in randomized trials. All data were analyzed on an intention-to-treat basis. We described the treatment effect of antibiotics on EOP using a risk ratio with 95% confidence intervals for treatment effect, and tested the effect using with the Chi-square or Fisher Exact test, the Mann-Whitney test for two independent samples, and or the Wilcoxon Signed-Ranks test for two paired samples, as appropriate. We considered two-tailed tests of significance with p<0.05 to be considered significant. All statistical analyses were performed using GraphPad Prism 8 (GraphPad Software Inc.) or SAS version 9.4 and R version 4.0.2.

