9.5. Resistome Assessment

Abundance of antibiotic resistance-associated genotypes in resistomes will be compared within and between treatment groups. If ceftriaxone or placebo alters resistomes, ANOVA will be performed across genotypes. The abundance of each genotype will be compared between ceftriaxone- and placebo-treated patients post-intervention by both Student's T test and $\chi 2$ to establish direct changes associated with ceftriaxone and whether those deviate from potential changes in resistomes due to ICU admission. All statistical analyses will be performed using GraphPad Prism 8 (GraphPad Software Inc). A p value <0.05 will be considered significant. To measure the acquisition of ARGs, the increase in number of ARGs relative to baseline samples were compared within each treatment group using the Wilcoxon Signed-Ranks test. In addition, the baseline number and changes in the number of ARGs targeting a prioridefined frequently administered (macrolides, beta-lactams, fluoroquinolones, sulfamethoxazole-trimethoprim, and vancomycin) and infrequently administered (tetracyclines, erythromycin, aminoglycosides, chloramphenicol, clindamycin, fosfomycin, quinupristin) antibiotics according to clinical practice guidelines were compared between treatment groups.^{67,68}

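### Section 9.5 has no between-arm test of overall resistance-gene acquisition, tests each genotype twice without error control, and cannot by difference tests alone support the no-harm expectation in section 2.7

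*Combined protocol and SAP*

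**What the plan says.** Section 9.5 contains five analytic statements on the resistome.

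- A general one: "Abundance of antibiotic resistance-associated genotypes in resistomes will be compared within and between treatment groups". No test is attached.
- A conditional one: "If ceftriaxone or placebo alters resistomes, ANOVA will be performed across genotypes". What counts as altered is not defined, and the ANOVA is not described as a gate for other tests.
- A per-genotype one: "The abundance of each genotype will be compared between ceftriaxone- and placebo-treated patients post-intervention", by both a t test and a chi-square test. Its purpose is to find changes tied to ceftriaxone and "whether those deviate from potential changes in resistomes due to ICU admission".
- An overall acquisition one: "the increase in number of ARGs relative to baseline samples were compared within each treatment group using the Wilcoxon Signed-Ranks test".
- A drug-group one: baseline numbers of ARGs and their changes, for antibiotics classed as often or seldom given "according to clinical practice guidelines were compared between treatment groups". No test is named.

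The threshold is p<0.05 throughout, and no multiplicity adjustment is stated. Section 9.2, in the sentence on the early-onset pneumonia (EOP) effect, lists "the Mann-Whitney test for two independent samples, and or the Wilcoxon Signed-Ranks test for two paired samples, as appropriate".

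Section 2.7 sets the expectation: "prophylactic ceftriaxone will not negatively affect bacterial resistomes as assessed by resistance genotypes in stool or sputum". Neither section gives a margin, a confidence-interval criterion or a power statement for the resistome.

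**The concern.** There are three separate faults.

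1. **Overall acquisition has no randomised contrast.** Patients in both arms are in the ICU, and section 2.5 notes that controls may receive longer courses of broad-spectrum antibiotics. ARG numbers may therefore rise in either arm for reasons unrelated to study drug. Only the difference between arms isolates ceftriaxone. A pair of within-arm p-values can suggest a contrast where there is none, or hide a real excess when both arms rise.
2. **Two tests per genotype.** With no deciding test and no control across genotypes, chance findings are expected and their number depends on an unstated rule.
3. **A no-harm expectation with difference tests only.** Failure to reject is not evidence of no effect, least of all in a trial sized for another outcome.

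The resistome is not a listed primary, secondary or safety outcome. It is, however, in the trial title and in section 2.7, section 11 puts it in the main publication, and section 2.2 names it as the risk to be weighed against benefit.

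**Working it through.** **Inputs.** From the documents: 60 per arm, 1:1 (section 9.1), and p<0.05 per test (section 9.5). Assumed, because no document gives them: normal change scores with SD 1; true changes of 0 to 1 SD; 40 per arm with paired swabs as a lower case (section 4.1 allows missing samples); 50 to 100 genotypes; chi-square applied to presence or absence.

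**The plan's own figure.** Section 9.5 has none. The only sample-size figure is for EOP: 55% versus 30%, 80% power, two-sided 5%. With pooled proportion 0.425:

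n = [1.96·√(2·0.425·0.575) + 0.8416·√(0.55·0.45 + 0.30·0.70)]² / 0.25² = (1.370 + 0.569)² / 0.0625 ≈ 60.2, so 61 per arm.

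The arcsine formula gives 60, and power at 60 is 79.9%. The figure reproduces, but it says nothing about the resistome.

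**Within-arm verdicts, same true change in both arms.** If each arm is significant with probability π, exactly one is significant with probability 2π(1−π), which peaks at 50% when π = 0.5. Simulation with Wilcoxon signed-rank tests (20,000 trials per setting) gave:

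| Shared change (SD) | Exactly one arm significant, 60 per arm | 40 per arm |
|---|---|---|
| 0 | 9.2% | 9.5% |
| 0.1 | 19.8% | 16.9% |
| 0.2 | 43.5% | 35.3% |
| 0.25 | 49.7% | 43.8% |
| 0.3 | 48.2% | 49.0% |
| 0.4 | 26.3% | 44.8% |
| 0.5 | 7.3% | 25.3% |
| 0.6 | 1.1% | 9.3% |

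Check at 0.25 SD and 60 per arm: a separate run gave π = 0.461, and 2·0.461·0.539 = 0.497. By symmetry, ceftriaxone alone is significant in half of these, about 25%. A between-arm Mann-Whitney test on the change scores rejected in 4.8% to 5.2% throughout.

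**Within-arm verdicts, arms truly different.**

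| Placebo vs ceftriaxone change (SD) | Per arm | Both arms significant | Between-arm test significant |
|---|---|---|---|
| 0.5 vs 0.8 | 60 | 95.9% | 36.0% |
| 0.5 vs 1.0 | 60 | 96.2% | 75.5% |
| 0.5 vs 0.8 | 40 | 85.1% | 25.3% |
| 0.5 vs 1.0 | 40 | 85.4% | 57.3% |

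The within-arm pair shows no contrast in most of these trials.

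**Genotypes, no true effect.** Expected false positives for one test: 50·0.05 = 2.5 to 100·0.05 = 5. If the genotypes were independent, the chance of at least one is 1−0.95^50 = 92% and 1−0.95^100 = 99.4%. The t test and chi-square are correlated. In simulation (60 per arm, prevalence 0.1 to 0.9, zero-inflated lognormal abundance), at least one was significant for 6.5% to 9.3% of null genotypes and both for 0.4% to 3.5%. Hence:

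- either test counts: 50·0.065 = 3.3 to 100·0.093 = 9.3 false positives;
- both required: 50·0.004 = 0.2 to 100·0.035 = 3.5.

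**No harm.**

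- 95% CI half-width, t·√(2/n): 1.980·√(2/60) = 0.36 SD; 1.991·√(2/40) = 0.45 SD.
- Two-sided t-test power for a 0.3 SD harm: 37.1% at 60 per arm and 26.3% at 40, so it is missed in 63% and 74%. For 0.5 SD: 77.5% and 59.8%, so missed in about 22% and 40%.
- Harm that could be excluded with 80% power if the true difference is zero, (1.96 + 0.8416)·√(2/n): 0.51 SD at 60 per arm, 0.63 SD at 40.

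**The case against.** **Between-arm work is planned.** The drug-group sentence compares changes in ARG number between arms and covers beta-lactams, the class that includes ceftriaxone. That is close to a between-arm acquisition analysis and could reveal an excess. This stands, and it would be wrong to say that section 9.5 lacks between-arm comparisons. But that sentence names no test and does not cover the total, and the genotype comparisons concern post-intervention abundance, not number acquired.

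**The aim of separating drug from ICU effects belongs to the genotype sentence.** Grammatically this is right. Even so, an acquisition result that cannot be attributed to either cause does not answer the section's question.

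**Section 9.2 already offers Mann-Whitney.** Neither rank test suits a binary, unpaired outcome such as EOP, so the list may be meant as a general one. That is plausible. If so, one sentence in section 9.5 settles it. As written, section 9.5 specifies its own test, and that test is within-arm.

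**The sizes rest on assumptions.** The plan does not say that one significant and one non-significant arm will be read as a treatment effect, and the 50% is the peak of a curve that falls to 1%. Gene counts are discrete, not normal. The false-positive range of 0.2 to 9.3 reflects an unknown genotype count and an unstated rule. All this is fair, and the figures should be read as ranges. The faults themselves do not depend on any one value.

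**Section 2.7 is an anticipated result, not a non-inferiority claim.** Correct. No passage says that p ≥ 0.05 will be taken as proof, so the third fault is a risk of misreading.

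**Conclusion.** The concern holds on all three parts. Section 9.5 names only a within-arm test for overall ARG acquisition. It tests every genotype by two methods at an unadjusted 0.05 with no deciding rule. It has no margin or interval criterion with which to support an expectation of no negative effect.

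Under normal change scores and 60 per arm, within-arm verdicts disagree in up to about half of trials when the arms do not differ, and agree in about 96% of trials when the arms differ as in the two cases examined. At 60 per arm the between-arm interval is about ±0.36 SD. Whether that is tight enough depends on a margin the documents do not give. The figures rest on assumed effect sizes, paired-sample numbers and 50 to 100 genotypes.

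The fault is confined to the resistome analysis. It does not touch the EOP comparison or its sample size. It should be corrected because the trial presents this analysis as the counterweight to any benefit.

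**What to change.** 1. Make the lead resistome analysis the between-arm difference in change from baseline in total ARG number in rectal swabs, from a baseline-adjusted count or rank model with a 95% CI. Name one lead time point. The 72–96 h swab, taken after study drug ends, is a reasonable choice, with 144–168 h as support. The plan ranks neither. Keep the within-arm Wilcoxon tests as description.
2. Name one test per genotype and control the false discovery rate at 5% by Benjamini-Hochberg, or label the genotype tests exploratory.
3. Report the between-arm CI and its upper limit. Do not conclude no negative effect from p ≥ 0.05 unless the sponsor states and justifies a margin.
4. Report by arm the numbers analysed and the reasons for missing 72–96 h swabs. Add a sensitivity analysis on the last available post-dose rectal swab.

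**Cost.** Analysis work only; samples and sequencing are unchanged. Fewer genotypes will be called significant. The lead analysis covers only patients with both swabs. Section 8.1 expects 40–50% in-hospital deaths (timing not given), section 4.1 ends sampling at death, comfort care or discharge, and section 9.7 commits only to considering imputation. The analysed group may therefore be selected and smaller than 60 per arm. The last-swab analysis mixes sampling times. Sections 4.2 and 9.5 are partly in the past tense and one reference carries a September 2024 access date. If the data have already been analysed, the new lead analysis must be labelled post hoc.

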9.6. Inflammation Assessment

We expect to obtain 56.3 \pm 4.5 x 10⁶ of total white blood cells, containing 14.7 \pm 1.7 x 10⁶ mononuclear cells and 6.3 \pm 1.1 x 10⁶ of CD3+ T cells from 10 mL of blood. We will use approximately 1 x 10⁶ CD3+ T cells to determine direct effects of ceftriaxone on CD73 expression and adenosine generation. We will use approximately 3 x 10⁶ of CD3+ T cells to isolate mRNA for gene expression analysis after treatment with ceftriaxone. Approximately 2-3 x 10⁶ whole blood cells will be used for flow cytometric analysis. Statistical analysis will be performed using the GraphPad Prism 7.0 software (GraphPad Software Inc). Comparisons between groups will be performed using two-tailed unpaired t tests. Comparisons between several groups will be performed using one-way ANOVA followed by appropriate post-hoc tests. A p value <0.05 will be considered significant.

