3.7. Randomization

A computer-generated allocation sequence will randomize patients in a 1:1 ratio in blocks of six. The clinical trials pharmacist at xxxx will be responsible for randomizing patients independent of study investigators. Based on the randomization, the clinical trials pharmacist will prepare the study drug blinded for delivery to the bedside nurse for administration. At non-xxxx hospitals, the investigators will contact the clinical trials pharmacist at xxxx, or their designee, to tell them of an enrollment. The xxxx clinical trials pharmacist will determine the subject number and complete the randomization.

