5.1. Specimen Handling and Transportation

Peripheral or arterial blood samples (10 mL) will be obtained at four time points for a total of up to 40 mL of blood. The four time points are: before study drug is administered (By 6 hours of ICU admission), 0-24 hours after administration of first dose of study drug, 48-72 hours after administration of first dose of study drug, and again 96-120 hours after administration of first dose of study drug . Missing time points does not disqualify patient for study participation and is not a protocol deviation. Sub-populations of

white blood cells will be measured using flow cytometry and mononuclear cells will be isolated using Ficoll-Paque[™]. Blood will not be collected if patient develops a hemoglobin less than 7 g/dL or requires a transfusion. COVID-19 considerations are outlined in Appendix 16.7. Blood specimens will be transported to xxxx for analysis. Samples from non-xxxx hospitals may be stored and transported under various conditions not listed above but that are acceptable.

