5.2. Effect of Ceftriaxone on CD73

CD3+ lymphocytes obtained from peripheral blood before administration of study drug will be adjusted to a concentration of 106 cell/mL and incubated with 50 mcg/mL ceftriaxone or vehicle for 24 hours. Expression of CD73 in subpopulations of CD3+ T cells will be determined using multi-parametric flow cytometry after staining cells with antibodies: CD3FITC-CD73PE-CD4PeCy7-CD8APC-CD39APC/Cy7-DAPI. CD73 levels in both CD4+ and CD8+ subpopulations of CD3+ T cells will be measured.

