8.1. Definitions

Adverse Event (per FDA 21CFR312.32)

Adverse event means any untoward medical occurrence associated with the use of a drug in humans, whether or not considered drug related.

Serious Adverse Event (per FDA 21CFR312.32)

An adverse event is considered "serious" if, in the view of either the investigator or sponsor (when applicable), it results in any of the following outcomes:

- Death (*see below exception)
- Life-threatening adverse event
- Inpatient hospitalization (*see below exceptions) or prolongation of existing hospitalization
- Persistent or significant incapacity or substantial disruption of the ability to conduct normal life functions (disability)
- Congenital anomaly/birth defect

Important medical events that may not result in death, be life-threatening, or require hospitalization may be considered serious when, based upon appropriate medical judgment, they may jeopardize the patient or subject and may require medical or surgical intervention to prevent one of the outcomes listed in this definition (above).

*Exception to the above serious adverse event definitions:

 An adverse event that results in death is usually considered a serious adverse event. However, 40-50% of patients who survive to the hospital after OHCA will not survive their hospital stay as a result of their underlying clinical condition. Since death is a clinical outcome for this study, deaths will not be reported as serious adverse events unless the investigator deems them related to study drug or study procedures.

Unexpected Adverse Event (per FDA 21CFR312.32)

An adverse event is considered "unexpected" if it is not listed in the investigator brochure or is not listed at the specificity or severity that has been observed; or, if an investigator brochure is not required or available, is not consistent with the risk information described in the general investigational plan or elsewhere in the current application, as amended.

Ceftriaxone is an FDA approved medication and does not have an investigator brochure. Therefore, the risk information is being provided in the protocol and informed consent form.

In addition, the unexpected adverse event definition assumes a causal relationship to the study drug (ceftriaxone). If an adverse event is not considered of Reasonable or Definite Relatedness to the ceftriaxone, it would not be considered an unexpected adverse event.

Relatedness

Relatedness	Description			

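### Section 9.6 does not say which inflammation comparison each test is for, leaves the pre-dose sample unused, and names no test for measurements on the same patient

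*Combined protocol and SAP*

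**What the plan says.** Section 9.6 is the only analysis text written for the inflammation work. It gives cell yields and their uses: some T cells are "to determine direct effects of ceftriaxone on CD73 expression and adenosine generation", others "to isolate mRNA for gene expression analysis after treatment with ceftriaxone". After naming the software it states the tests: "Comparisons between groups will be performed using two-tailed unpaired t tests" and "Comparisons between several groups will be performed using one-way ANOVA followed by appropriate post-hoc tests". It does not say which arm, assay, time point or culture condition each test is for.

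Section 5 describes these measurements:

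- **5.1:** four blood samples per patient, one before study drug and three after. On gaps it says "Missing time points does not disqualify patient for study participation and is not a protocol deviation".
- **5.2:** T cells taken before study drug, "incubated with 50 mcg/mL ceftriaxone or vehicle for 24 hours".
- **5.3:** adenosine production in three T-cell populations.
- **5.4:** gene expression under vehicle, ceftriaxone and a combination with AMP.
- **5.5:** flow cytometry before study drug and on study days 1 and 3.

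The trial has two arms (3.7): "A computer-generated allocation sequence will randomize patients in a 1:1 ratio in blocks of six". A signed-rank test for paired data appears in 9.2, under the primary outcome, and in 9.5, for change from baseline in resistance genes. Section 9.6 does not mention it.

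**The concern.** Two things are left open.

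First, the arm comparison. The pre-dose blood sample is part of the schedule, yet an unpaired t test on a post-dose value makes no use of it. Precision is given up although the sample is already planned.

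Second, the reach of the named tests. With two arms, the several groups meant for one-way ANOVA cannot be the arms alone. The sets of three that section 5 offers are cell populations, culture conditions and time points. Populations and time points come from the same patients. For the cultures, splitting one patient's cells is the plain reading of 5.2 and 5.4 but is not stated. An unpaired test or one-way ANOVA on such matched data leaves between-patient variation in the error term.

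Less T cell-mediated inflammation is part of the study hypothesis (2.7), and the inflammation data go into the main publication (11). It is not a listed outcome in 3.11. What is at stake is missing a modest real effect in the mechanistic work, and a choice of test left open until data are seen.

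**Working it through.** **The plan's own figure.** The documents give no power figure for inflammation. The only one is for the primary outcome (9.1): 80% power with 60 per arm for 55% versus 30%. The pooled-variance formula for two proportions gives 79.9%, so it reproduces and is not in dispute.

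**Inputs.** From the documents: 60 patients per arm, 120 in all (9.1), and two-sided 0.05 (9.6). Assumed, because the documents give none of them: normal data with equal variances, correlation r = 0.3, 0.5 or 0.7 between measurements on the same patient, effects of 0.2 to 0.5 SD, and either 120 or 60 patients with usable cells.

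**1. Arm comparison, 60 versus 60, one post-dose time.** The standard error of the unpaired difference is SD x sqrt(2/60) = 0.183 SD. Adjusting for the pre-dose value multiplies it by sqrt(1 - r^2). Power for 0.5 SD is from the noncentral t distribution.

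| r | SE multiplier | Unpaired t | Adjusted |
|---|---|---|---|
| 0.3 | sqrt(0.91) = 0.95 | 78% | 81% |
| 0.5 | sqrt(0.75) = 0.87 | 78% | 88% |
| 0.7 | sqrt(0.51) = 0.71 | 78% | 97% |

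Simulation (20,000 data sets) gave 77-78% unpaired and 81%, 87% and 97% adjusted. Both methods kept a type I error of about 5%.

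**2. Two matched conditions, 120 patients.** The true standard error of the mean difference is SD x sqrt(2(1 - r)/n). The unpaired test uses SD x sqrt(2/n), which is too large. It therefore rejects only when the correctly scaled statistic exceeds about 1.970/sqrt(1 - r), which is 2.355, 2.786 and 3.597 for the three values of r. Under no effect, the nominal 5% test runs at about 1.9%, 0.5% and below 0.1%.

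The paired test has noncentrality d x sqrt(n/(2(1 - r))). For d = 0.3 this is 0.3 x sqrt(120/1.4) = 2.78, then 3.29 and 4.24. Simulated power (40,000 data sets), unpaired versus paired:

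| Effect, patients | r = 0.3 | r = 0.5 | r = 0.7 |
|---|---|---|---|
| 0.2 SD, n = 120 | 31 vs 45% | 28 vs 58% | 23 vs 80% |
| 0.3 SD, n = 120 | 66 vs 79% | 69 vs 90% | 73 vs 99% |
| 0.5 SD, n = 120 | 99 vs 100% | 100 vs 100% | 100 vs 100% |
| 0.3 SD, n = 60 | 35 vs 49% | 32 vs 63% | 28 vs 84% |

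The formulas agree with the n = 120 rows to within about one point. A second simulation gave 74% for the unpaired test at 0.3 SD and r = 0.7. With r = 0 there is no loss.

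**3. Three matched conditions, 120 patients, shifts 0, 0.2 and 0.2 SD.** One-way ANOVA has power 28%, 23% and 15% (20,000 data sets). An analysis with a patient effect has 47%, 61% and 84%.

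**The case against.** The strongest reply is that 9.6 never assigns unpaired tests to matched cells. Elsewhere in the plan a group is mostly a randomized arm, and between arms the unpaired t test is valid. Several groups could mean arms split by a patient characteristic, which would be independent. The cell-yield sentences describe sample use and are separated from the tests by a sentence on software. This stands, and it is why the second half of the point is conditional. But if groups means arms only, the same-patient comparisons in 5.2, 5.4 and 5.5 have no stated test.

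A second reply is that the signed-rank test in 9.2 is general wording: pneumonia is a yes/no outcome in independent arms, so that test has no use there. This weakens any claim that paired analysis is excluded. It does not settle the matter, because the sentence is about pneumonia and 9.6 names its own tests, software and significance level. Section 9.7 (report missing data, consider multiple imputation) does not choose a test either.

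Third, adjusting for the pre-dose value improves efficiency and does not correct an invalid test. That is accepted.

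Two stronger readings are tempting. A reader might infer inflated false positives, since treating a patient's repeated samples as independent in an arm comparison would have that effect. The plan nowhere proposes it. A reader might also take the 8.1 statement that "40-50% of patients who survive to the hospital after OHCA will not survive their hospital stay" as the expected loss of samples. That figure covers the whole hospital stay, while the last blood sample is due by 120 hours. Section 3.2 also excludes patients unlikely to survive 48 hours after return of circulation, and 3.14 provides at least 72 hours of treatment with stated exceptions.

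**Conclusion.** The point holds as a minor one. Section 9.6 should link tests to comparisons, and two better methods are available at almost no cost.

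For the arms, the planned test is valid but less precise than the schedule allows. The gain at 0.5 SD is about 3, 10 or 19 percentage points of power for r of 0.3, 0.5 or 0.7.

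For same-patient data, if the named tests are used there, the error is conservative under positive correlation. At 120 patients the loss is large for effects of 0.2 to 0.3 SD and negligible at 0.5 SD. With fewer usable samples it reaches larger effects: at 60 patients and 0.5 SD, power is 82%, 85% and 91% unpaired against 90%, 97% and nearly 100% paired.

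All sizes rest on assumed correlations, effects and usable numbers. The documents do not show that a wrong test has been assigned to matched cells, nor that the randomized comparison is invalid. The primary outcome and the sample size are unaffected.

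**What to change.** State in 9.6 which method goes with which comparison:

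1. **Ceftriaxone versus placebo arms:** ANCOVA at one named post-dose time, or a mixed model over the post-dose times, with the pre-dose value as covariate. Say how patients without a pre-dose sample are kept in.
2. **Two culture conditions on one patient's cells (5.2):** paired t test or signed-rank test.
3. **Three or more conditions on one patient's cells (5.4):** a model with a patient effect.
4. **Change over time (5.1, 5.5):** a mixed model on all available samples, because 5.1 allows missed samples and standard repeated-measures ANOVA would drop incomplete patients.

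If 5.2 or 5.4 does not split one patient's cells, say so; the unpaired test then stands there.

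The cost is wording and a little analysis work, with no new samples or assays. The mixed models may need the SAS or R named in 9.2 in place of the Prism version named in 9.6. Parts of the plan are in the past tense, so if any inflammation data have been analysed, label the change as post hoc.
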